12.5 Interim Analysis

We will primarily conduct analysis and track AE/SAEs in anticipation of our DSMB meetings. We will also conduct analysis of the primary and secondary endpoints. The DSMB will review the study outcomes in an unmasked fashion (study is not blinded).

12.6 Reporting and Exclusions

12.6.1 Evaluation of Toxicity

Not applicable

12.6.2 Evaluation of Response

Not applicable.

13. Adverse Event Reporting Requirements

Adverse event (AE) monitoring and reporting is a routine part of every clinical trial. The investigator will be required to provide appropriate information concerning any findings that suggest significant hazards, contraindications, side effects, or precautions pertinent to the safe use of the drug or device under investigation. Safety will be monitored by evaluation of adverse events reported by subjects or observed by investigators or research staff.

13.1 Adverse Event Definition

An adverse event (also referred to as an adverse experience) can be any unfavorable and unintended sign (e.g., an abnormal laboratory finding), symptom, or disease temporally associated with the use of a drug and does not imply any judgment about causality. An adverse event can arise with any use of the drug (e.g., off-label use, use in combination with another drug) and with any route of administration, formulation, or dose, including an overdose.

13.1.1 Investigational Agent or Device Risks (Expected Adverse Events)

Adverse events are not expected, but the following are risks are possible:

- i) Risks associated with down-titration/discontinuation of beta-blocker: Adverse drug titration events including tachycardia, worsened hypertension, palpitations, diaphoresis, and shortness of breath, heart failure exacerbation, angina, myocardial infarction, cerebrovascular accident, arrhythmia, hospitalization, and death (shown to occur with abrupt cessation of beta-blocker)
- ii) Risks associated with beta-blocker use (and re-initiation/up-titration): Adverse drug events or adverse drug reactions including bradycardia, heart block, hypotension, dizziness, fatigue, depression, confusion, heart failure exacerbation, cerebrovascular accident, hospitalization, and death
- iii) Risks associated with wearing the Garmin wearable device: Local skin irritation, wrist pain
- iv) Risks associated with subject interviews: Emotional distress related to answering interview questions, and breach of confidentiality
- v) Risks associated with CPETs: musculoskeletal injury, arrhythmias, acute coronary syndrome, hemodynamic instability, cardiovascular collapse, death
- vi) Risks associated with Short physical performance battery: falling, musculoskeletal injury.
- vii) Risks associated with the 6-minute walk test: fatigue, dizziness.
- viii) Risks associated with blood draws: pain or bruising, dizziness, infection at the site of the blood draw

13.1.2 Adverse Event Characteristics and Related Attributions

The following procedures will be used to document adverse events:

A vignette will be created describing the i) date of the event, ii) the date that study personnel became aware of the event, iii) clinical circumstances surrounding the event including precipitating events, iv) action taken by study personnel including treatment, and v) outcome of the event. This will be documented by PI [name].

Adverse events will be graded per Common Terminology Criteria for Adverse Events version 5.0 criteria. Grade refers to the severity of the AE.

Grade 1: Mild; asymptomatic or mild symptoms; clinical or diagnostic observations only; intervention not indicated

Grade 2: Moderate; minimal, local or noninvasive intervention indicated; limiting age-appropriate instrumental ADL⁷

Grade 3: Severe or medically significant but not immediately life-threatening; hospitalization or prolongation of hospitalization indicated; disabling; limiting self-care ADL⁸

Grade 4: Life-threatening consequences; urgent intervention indicated

Grade 5: Death related to AE

Relatedness of the AE: This will be determined by [name], by using the following:

- Definitely Related
- Probably Related
- Possibly Related
- Not Related to the Research

Expectedness of the AE: This will be determined by [name] (Yes/No):

- Unexpected: Those that differ from AEs highlighted in Section 13.1.1 in nature, severity or frequency
- Expected: Those consistent with AEs highlighted in Section 13.1.1 in nature, severity, or frequency

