13.1.4 Reporting of AE to WCM IRB and DSMB

All AEs occurring on this study will be reported to the WCM IRB according to the WCM IRB policy, which states that **expected and unexpected** adverse events, grades 3-5, should be reported on the Adverse Event & IND Safety Reporting Cumulative Table. These AEs will be reported at continuing review.

Adverse events which meet ALL of the following 3 conditions will be reported within 7 calendar days of PI awareness:

1. The harm is “unexpected” when its specificity and severity are not reflected in the informed consent form; AND
2. The harm is “related” or “possibly related” AND
3. The harm that places subjects at a greater risk of harm than previously known or recognized

⁷ Instrumental ADL refers to preparing meals, shopping for groceries or clothes, using the telephone, managing money, etc.

⁸ Self-care ADL refers to bathing, dressing and undressing, feeding self, using the toilet, taking medications, and not bedridden.

WCM DSMC

All Adverse events which meet ALL of the following 3 conditions will be reported within 7 calendar days of PI awareness:

1. The harm is “unexpected” when its specificity and severity are not reflected in the informed consent form; AND
2. The harm is “related” or “possibly related” AND
3. The harm that places subjects at a greater risk of harm than previously known or recognized

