13.2.1 Reporting of SAE to IRB & DSMC

WCM IRB:

All SAEs occurring in this study will be reported to the IRB according to the IRB policy. IRB policy states that SAEs should be reported within 7 days if the following criteria are met:

- The SAE is unexpected and not reflected in the ICF
- The SAE is related or possibly related
- The SAE places subjects at a greater risk of harm than previously known or recognized

At yearly continuing reviews, all AEs and SAEs grade 3-5 that are either expected or unexpected must be reported.

WCM DSMC:

Immediate reports for SAEs will be submitted to the DSMC within 7 calendar days of PI awareness if they meet all the following criteria:

1. The harm is “unexpected” when its specificity and severity are not reflected in the informed consent form; AND
2. The harm is “related” or “possibly related” AND
3. The harm that places subjects at a greater risk of harm than previously known or recognized

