14.1.2 Unanticipated Problem Reporting

The investigator will report unanticipated problems (UPIRTSOs) to the reviewing Institutional Review Board (IRB). The UPIRTSO report will include the following information:

- Protocol identifying information: protocol title and number, PI’s name, and the IRB project number;
- A detailed description of the event, incident, experience, or outcome;
- An explanation of the basis for determining that the event, incident, experience, or outcome represents an UPIRTSO;
- A description of any changes to the protocol or other corrective actions that have been taken or are proposed in response to the UPIRTSO.

To satisfy the requirement for prompt reporting, UPIRTSOs will be reported using the following timeline:

- UPIRTSOs that are serious adverse events (SAEs) will be reported to the IRB and to the DSMB within 3 days of the investigator becoming aware of the event.
- Any other UPIRTSO will be reported to the IRB and to the DCC/study sponsor within 7 days of the investigator becoming aware of the problem.

15. Data and Safety Monitoring Plan (DSMP)

We plan to use the WCM DSMB for this trial, as this a resource provided to the WCM scientific community, and they have the necessary expertise and infrastructure to act as a DSMB for this trial. All AEs and SAEs will be reported to the DSMB. AEs where the harm is unexpected, the harm is “related” or “possibly related,” and the harm suggests that the research places subjects at greater risk of harm than previously known, an immediate report will be submitted within 7 calendar days of the PI awareness. We will record seriousness, relatedness and expectedness of the adverse event, as determined by [name]. We will

report when the AE occurred, as well as when the study team became aware of the AE. We will collect any medical documentation pertaining to the AE. If treatment must be stopped, this determination will be made by [name] with the subject. Because all subjects will have been on study drug before initiating the trial, and we will not exceed their home dose, we do not anticipate having to terminate study treatment.

The DSMB will convene to review the study data after each cohort of 4 subjects.

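### No timed report to the DSMB is triggered by death or seriousness alone: every timed route requires the event to be unexpected, a term the protocol defines in three different ways

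*Combined protocol and SAP*

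**What the plan says.** Section 13.1.1 carries the words Expected Adverse Events in its heading. Under down-titration and discontinuation it lists, among others, "heart failure exacerbation, angina, myocardial infarction, cerebrovascular accident, arrhythmia, hospitalization, and death (shown to occur with abrupt cessation of beta-blocker". Its opening sentence nevertheless says that adverse events are not expected.

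Section 13.1.2 sorts events by comparison with that list: "Expected: Those consistent with AEs highlighted in Section 13.1.1 in nature, severity, or frequency" and "Unexpected: Those that differ from AEs highlighted in Section 13.1.1 in nature, severity or frequency". One assessor makes the yes/no call.

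Section 13.1.4 sets the expedited rule: "Adverse events which meet ALL of the following 3 conditions will be reported within 7 calendar days of PI awareness". The three conditions are that the harm is unexpected, that it is related or possibly related, and that it raises the risk to subjects beyond what was already recognised. Here, harm is unexpected "when its specificity and severity are not reflected in the informed consent form". Section 13.2.1 applies the same three conditions to serious events: "Immediate reports for SAEs will be submitted to the DSMC within 7 calendar days of PI awareness if they meet all the following criteria".

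Section 14.1 defines unanticipated problems (UPIRTSOs), which must also be unexpected. Section 14.1.2 sends those that are SAEs to the IRB and DSMB within 3 days. Section 15 repeats the 7-day rule with the same three conditions and states, without a deadline, that all adverse events go to the DSMB. It then adds: "The DSMB will convene to review the study data after each cohort of 4 subjects".

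**The concern.** The trial withdraws a cardiac drug from patients aged 65 or over with heart failure. The events most likely to make a monitoring board want to look at the study are death, myocardial infarction and stroke during the taper. The protocol places exactly these on its list of expected events, and then makes unexpectedness a precondition of every dated report. If such an event is classed as expected, no dated duty to inform the board remains. Because the classification rests on three wordings that do not agree, two careful readers could send the same death down different routes.

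**Working it through.** There is no stated figure to reproduce. The check traces the reporting routes and then works out the timing. The protocol uses both DSMB and DSMC; I treat them as one body, as the heading of 13.1.4 suggests.

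**Step 1. Routes open to a related death during down-titration**

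| Route | Section | Clock | Must be unexpected? | Judged against |
|---|---|---|---|---|
| AE report to IRB and DSMC | 13.1.4 | 7 days | Yes | Consent form |
| SAE report to IRB and DSMC | 13.2.1 | 7 days | Yes | Consent form |
| UPIRTSO that is an SAE, to IRB and DSMB | 14.1, 14.1.2 | 3 days | Yes | Protocol-related documents and subject population |
| Immediate report | 15 | 7 days | Yes | Not stated there; 13.1.2 is the general definition |
| All AEs and SAEs to DSMB | 13.1.5, 15 | None | No | n/a |
| DSMB meeting | 15 | After each cohort of 4 | No | n/a |
| Grade 3-5 events to IRB | 13.1.4, 13.2.1 | Continuing review (yearly) | No | n/a |

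Each of the four timed routes also requires the event to suggest a greater risk than was already recognised. Death or seriousness alone opens none of them.

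**Step 2. How the death would be classified**

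- Under 13.1.2, both definitions join nature, severity and frequency with *or*. A death matches the list in nature and severity, so it is Expected. If it is thought more frequent than the list implies, it is also Unexpected. Section 13.1.1 gives no frequencies, so that part of the test cannot be applied.
- Section 13.1.1 ties its list to abrupt cessation, whereas this trial tapers, and it says adverse events are not expected. Either point could support calling a taper death unexpected.
- Under 13.1.4 and 13.2.1 the answer depends on the consent form, which is not in the text reviewed. Section 2.3.1 lists the same risks, including death. If the form follows it, the death would probably count as expected.
- Under 14.1 the judgement takes in the population as well as the documents, so it is not simple membership of a list.

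The classification is therefore open, and *expected* is an available answer on each wording.

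**Step 3. Time to the next cohort meeting**

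Inputs: one subject per month (12.2), or 16 subjects over a 30-month enrollment period (synopsis), which is 30/16 = 1.875 months per subject; periods of up to 6 weeks, 2 to 6 of them (3.1); 365.25/12/7 = 4.348 weeks per month.

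*Meeting after the fourth subject completes.* Take an event at week 6 of the cohort's first subject, the end of the first Off period in Arm 2. With m months per subject and p periods:

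wait = 3 × m × 4.348 + 6p − 6 weeks

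| m | 3 × m × 4.348 | p = 2 | p = 4 | p = 6 |
|---|---|---|---|---|
| 1 | 13.04 | 19.0 | 31.0 | 43.0 |
| 1.875 | 24.46 | 30.5 | 42.5 | 54.5 |

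Unrounded, the extremes are 19.04 and 54.46, so about 19 to 54 weeks.

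*Meeting after the fourth subject enrols.* Spacing = 4 × m × 4.348 = 17.4 weeks (m = 1) or 32.6 weeks (m = 1.875), so about 17 to 33 weeks apart.

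**The case against.** A reader might infer that a death in the taper counts as expected, fails the expedited test and must wait most of a year for the board. The documents do not support that, for four reasons.

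- The 7-day tests in 13.1.4 and 13.2.1 do not use the 13.1.2 definition. They refer to the consent form, whose content cannot be checked here.
- The overlap in 13.1.2, the opening sentence of 13.1.1 and its reference to abrupt cessation make the classification ambiguous, not settled. An assessor could call the event unexpected and start the 3-day or 7-day clock.
- A meeting is not a report. All adverse events must go to the DSMB, and nothing holds them back until a cohort closes. The DSMB also has a consulting role on red flags (6.1.2a) and may be consulted when a subject is withdrawn for an adverse event (8.2).
- Section 15 does not say whether a cohort's review follows enrolment or completion, and the number of periods varies, so no single waiting time can be given.

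All four points stand, and they limit the finding to what the text permits. None supplies a deadline. The general duty allows prompt reporting without requiring it. The red-flag and withdrawal provisions concern the handling of an individual subject and set no reporting time for a death.

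**Conclusion.** The gap is real but conditional. A related death, myocardial infarction or stroke during the taper *could* be judged expected, and the DSMB would then be owed only an untimed report and its next cohort meeting. Against conditional clocks of 3 or 7 days, the backstop is about 19 to 54 weeks on the completion reading, or meetings about 17 to 33 weeks apart on the enrolment reading.

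The completion figures are for an event at week 6 of a cohort's first subject, with no replacement of subjects under 8.2. A later event, or one in a later subject of the cohort, would wait less; an earlier one would wait longer. The routing result does not depend on these assumptions. It follows from the conditions attached to each timed route. This is a cheap improvement to safety oversight; it does not show that the board would in fact be left uninformed.

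**What to change.** 1. In the DSMB/DSMC parts of 13.1.4 and 13.2.1, and in section 15, add that every fatal or life-threatening SAE, and every myocardial infarction or stroke, goes to the DSMB on the existing expedited timeline. State that this applies regardless of expectedness and of the condition about risk beyond what was already known; lifting only the first would leave the second able to exclude a listed event. Leave the IRB criteria as they are, since the protocol presents them as institutional policy.
2. Use one non-overlapping definition of unexpected in 13.1.2, 13.1.4, 13.2.1, 14.1 and 15. Drop the frequency term or state a reference frequency. Changing *or* to *and* in 13.1.2 alone is not enough: it does not reach the consent-form tests, and it cannot be applied on frequency while 13.1.1 gives none.

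While editing, reconcile the heading and opening sentence of 13.1.1, and say in section 15 whether a cohort's review follows enrolment or completion.

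The cost is protocol wording and a few more expedited reports in a 16-subject study.

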13.1.3 Recording of Adverse Events

All adverse events will be recorded on a subject specific AE log. The AE log will be maintained by the research staff and kept in the subject's research chart.

13.1.4 Reporting of AE to WCM IRB and DSMB

All AEs occurring on this study will be reported to the WCM IRB according to the WCM IRB policy, which states that **expected and unexpected** adverse events, grades 3-5, should be reported on the Adverse Event & IND Safety Reporting Cumulative Table. These AEs will be reported at continuing review.

Adverse events which meet ALL of the following 3 conditions will be reported within 7 calendar days of PI awareness:

1. The harm is “unexpected” when its specificity and severity are not reflected in the informed consent form; AND
2. The harm is “related” or “possibly related” AND
3. The harm that places subjects at a greater risk of harm than previously known or recognized

⁷ Instrumental ADL refers to preparing meals, shopping for groceries or clothes, using the telephone, managing money, etc.

⁸ Self-care ADL refers to bathing, dressing and undressing, feeding self, using the toilet, taking medications, and not bedridden.

WCM DSMC

All Adverse events which meet ALL of the following 3 conditions will be reported within 7 calendar days of PI awareness:

1. The harm is “unexpected” when its specificity and severity are not reflected in the informed consent form; AND
2. The harm is “related” or “possibly related” AND
3. The harm that places subjects at a greater risk of harm than previously known or recognized

13.1.5 Reporting Events to Subjects

Not applicable. We are not performing diagnostic studies; we do not anticipate any incidental findings.

AEs and SAEs will not be reported directly to subjects, unless otherwise instructed to by the DSMB. (All AEs and SAEs will be reported to the DSMB.)

13.1.6 Events of Special Interest

Not applicable.

13.1.7 Reporting of Pregnancy

Not applicable.

13.2 Definition of SAE

An SAE is defined by the ICH guidelines as any AE fulfilling at least one of the following criteria:

- Fatal
- Life threatening: refers to an event in which the subject was at risk of death at the time of the event. It does not refer to an event that hypothetically might have caused death had it been more severe
- Requiring in-patient hospitalization or prolongation of existing hospitalization.
- Resulting in persistent or significant disability or incapacity
- Congenital anomaly or birth defect
- Medically significant: refers to important medical events that may not immediately result in death, be life-threatening, or require hospitalization but may be considered to be SAEs when, based upon medical judgement, they may jeopardize the subject, and may require medical or surgical intervention to prevent one of the outcomes listed in the definitions above.

The following reasons for hospitalization are not considered as SAEs:

- Hospitalization for cosmetic elective surgery, or social and/or convenience reasons
- Hospitalization for pre-planned surgery or standard monitoring of a pre-existing disease or medical condition that did not worsen

13.2.1 Reporting of SAE to IRB & DSMC

WCM IRB:

All SAEs occurring in this study will be reported to the IRB according to the IRB policy. IRB policy states that SAEs should be reported within 7 days if the following criteria are met:

- The SAE is unexpected and not reflected in the ICF
- The SAE is related or possibly related
- The SAE places subjects at a greater risk of harm than previously known or recognized

At yearly continuing reviews, all AEs and SAEs grade 3-5 that are either expected or unexpected must be reported.

WCM DSMC:

Immediate reports for SAEs will be submitted to the DSMC within 7 calendar days of PI awareness if they meet all the following criteria:

1. The harm is “unexpected” when its specificity and severity are not reflected in the informed consent form; AND
2. The harm is “related” or “possibly related” AND
3. The harm that places subjects at a greater risk of harm than previously known or recognized

13.2.2 Reporting of SAE to FDA [For Protocols Where WCMC is the Sponsor-Investigator]

Not applicable.

13.3 AE/SAE Follow Up

In addition to reporting all adverse events, the study team will take all appropriate measures to ensure that subjects will have access to necessary medical care. Any acute change in medical condition will be reported to the subject's physician for follow-up care. All information about the study will be provided to the caring physician. As this study is not blinded, there will be no masking issue with regard to providing optimal medical care. All study procedures will be discontinued at the treating physician's request, the subject's request, and/or as judged appropriate by the principal investigator. In the case of any emergency situation, the study physicians will institute any emergency aid needed and then make arrangements for transportation to the Emergency Department. All research subjects will have access to medical care if an adverse event occurs. The subject and/or the insurance carrier will be billed for this care. Subjects will not receive special compensation for injury solely because they are subjects in the study. All subjects are fully informed about this policy as part of the informed consent process.

For SAEs that are determined to be “possibly related” or “related”, the subject will be assessed, evaluated, and treated for any potential recurrence and according to the seriousness of the symptoms. Based on the information gathered, it will then be determined whether the subject should be removed from the study or continue their participation.

13.4 Time Period and Frequency for Event Assessment and Follow Up

The occurrence of an adverse event (AE) or serious adverse event (SAE) may come to the attention of study personnel during study visits and interviews of a study subject presenting for medical care, or upon review by a study monitor.

All AEs including local and systemic reactions not meeting the criteria for SAEs will be captured on the appropriate case report form (CRF). Information to be collected includes event description, time of onset, clinician's assessment of severity, relationship to study product (assessed only by those with the training and authority to make a diagnosis), and time of resolution/stabilization of the event. All AEs occurring while on study must be documented appropriately regardless of relationship. All AEs will be followed to adequate resolution.

Any medical condition that is present at the time that the subject is screened will be considered as baseline and not reported as an AE. However, if the study subject's condition deteriorates at any time during the study, it will be recorded as an AE.

Changes in the severity of an AE will be documented to allow an assessment of the duration of the event at each level of severity to be performed. AEs characterized as intermittent require documentation of onset and duration of each episode.

The study coordinator or the principal investigator will record all reportable events with start dates occurring any time after informed consent is obtained until 7 (for non-serious AEs) or 30 days (for SAEs) after the last day of study participation. At each study visit, the investigator will inquire about the occurrence of AE/SAEs since the last visit. Events will be followed for outcome information until resolution or stabilization. The following table provides examples of actions that may be taken following selected adverse events.

| Adverse Event | Typical Action |
|----------------------------|---|
| Hospitalization | Medical management including beta-blocker management as recommended by treating physician. If hospitalization unrelated to study and not contraindicated following discussion between investigators and hospital care team, subject will continue to follow protocol while hospitalized. |
| Worse or new arrhythmia | Emergent care if indicated including admission and necessary medications/interventions. Subject withdrawal from the study. |
| Cerebrovascular accident | Emergent care if indicated including admission and necessary medications/interventions. Subject withdrawal from the study. |
| Myocardial infarction | Emergent care if indicated including admission and necessary medications/interventions. Subject withdrawal from the study. |
| Angina | Emergent care if indicated including admission and necessary medications/interventions. Subject withdrawal from the study. |
| Heart failure exacerbation | Emergent care if indicated including admission and IV diuretics. For non-emergent issues, standard review and adjustment of medications. Medical management including beta-blocker management as recommended by treating physician. If exacerbation unrelated to the study and not contraindicated following discussion between investigators and treating physician, subject will continue to follow protocol. |
| Shortness of breath | Evaluation of volume status, adjustment of medications. Medical management including beta-blocker management as recommended by treating physician. If exacerbation unrelated to the study and not contraindicated following discussion between investigators and treating physician, subject will continue to follow protocol. |
| Worsened hypertension | Emergent care if indicated including admission and IV antihypertensive agents. For non-emergent issues, standard review and management of oral medications. If unrelated to the study and not contraindicated following discussion between investigators and treating physician, subject will continue to follow protocol. |

14. Unanticipated Problems Involving Risks to Subjects or Others

